9.3.2 CLINICAL EVENTS COMMITTEE

A separate Clinical Events Committee (CEC) composed of 2 independent cardiologists/ electrophysiologists will adjudicate all ICD events in this study.

9.3.3 DATA SAFETY MONITORING BOARD

To meet the study's ethical responsibility to its subjects, an independent data safety monitoring board (DSMB) will monitor results during the study. The DSMB will act in a senior advisory capacity to the DCC regarding data and safety matters throughout the duration of the study. In addition, the DSMB will review interim summary results of the accumulating data from the Clinical Events Committee every 6 months or as needed. These data include adverse events (e.g., infection, bleeding, right heart failure) and mortality. They will communicate their findings directly with the DCC. The FDA will be provided a copy of any written communication from the DSMB to the study sponsor related to safety concerns, or changes to the study protocol, procedures or informed consent document. The DSMB will be provided a copy of any letter from the FDA to the study sponsor related to safety concerns, or changes to the study protocol, procedures or informed consent document. The clinical centers will have no contact with the members of DSMB regarding this trial and no voting member of the committee may participate in the study as an investigator. Non-DSMB members will not be allowed during DSMB closed meetings. However, the PI will only be present at the open session of the meetings to clarify questions concerning the protocol and to provide updates to the DSMB regarding pertinent new trial information. However, recommendations and decisions regarding the study are solely up to the discretion of the DSMB. The DSMB will be composed of 2 cardiologists, 1 electrophysiologist, 1 nephrologist and 1 biostatistician.

9.4 RISKS

ICD implantation will occur according to standard procedure, and therefore the risk includes that of a standard ICD implantation. In addition, the risks of the renal sympathetic ablation and renal angiography procedure include:

Common:

- Discomfort at the site of vascular access
- Groin hematoma

Uncommon:

- Bleeding
- Vascular injury
- Renal artery dissection
- Renal artery stenosis or occlusion
- Thromboembolism, including renal infarction and peripheral atheroembolism. This risk is minimized considerably by the short duration of the procedure, as well as the use of a saline-irrigated ablation catheter.
- Risks associated with sedatives/anesthesia.
- Injury to adjacent structures (phrenic nerve, cardiac valves)
- Renal dysfunction potentially needing hemodialysis
- Vascular complications (including pseudoaneurysm, AV fistula requiring surgical intervention)
- Radiation burns
- Pneumonia and/or sepsis
- Death

An adverse event is any undesirable clinical occurrence in a study patient, whether or not it is related to the study intervention. Any condition that was recorded as pre-existing is *not* an AE unless there is a change in the nature, severity or degree of the condition.

9.4.1 SERIOUS ADVERSE EVENTS

Serious adverse events are defined by FDA regulation as any experience that results in a fatality or is life threatening; results in significant or persistent disability; requires or prolongs a hospitalization; results in a congenital anomaly/birth defect; or represents other significant hazards or potentially serious harm to research subjects or others, in the opinion of the investigators. Important medical events that may not result in death, be life-threatening, or require hospitalization may be considered a serious adverse event when, based upon appropriate medical judgment, they may jeopardize the patient and may require medical or surgical intervention to prevent one of the outcomes listed in this definition. Examples of such medical events include bronchospasm requiring intensive treatment in an emergency room or at home, blood dyscrasias, or convulsions that do not result in inpatient hospitalization.

9.4.2 UNANTICIPATED SERIOUS ADVERSE EVENTS

An unanticipated (unexpected) serious adverse event is any serious adverse event that is not protocol-defined or documented in the patient consent form. Expedited reporting is required for serious adverse events that are unexpected.

9.4.3 UNANTICIPATED ADVERSE DEVICE EFFECTS

An unanticipated adverse device effects (UADE) is any serious adverse effect on health or safety or any life-threatening problem caused by, or associated with, a device, if that effect, problem, or death was not previously identified in nature, severity, or degree of incidence in the investigational plan, or any other unanticipated serious problem associated with the device that relates to the rights, safety, or welfare of subjects.

9.4.4 UNANTICIPATED PROBLEMS

According to the Office for Human Research Protections (*OHRP*), an Unanticipated Problem (UP) generally includes any incident, experience, or outcome that meets **all** of the following criteria: (1) Unexpected (in terms of nature, severity, or frequency) given (a) the research procedures that are described in the protocol-related documents, such as the IRB-approved research protocol and informed consent document; and (b) the characteristics of the subject population being studied; *and* (2) Related or possibly related to participation in the research (in this guidance document, *possibly related* means there is a reasonable possibility that the incident, experience, or outcome may have been caused by the procedures involved in the research); *and* (3) Suggests that the research places subjects or others at a greater risk of harm (including physical, psychological, economic, or social harm) than was previously known or recognized.

Based on the definitions above and as illustrated below (per OHRP guidance), many adverse events are not unanticipated problems, and many unanticipated problems are not adverse events. However, some adverse events are also unanticipated problems. For example, a serious adverse event that is unexpected and at least possibly related to study participation is also by definition an unanticipated problem. As stated above, an unanticipated problem may not necessarily be an adverse event, which is the case when the problem does not cause actual physical harm to participants. For example, if a laptop computer with sensitive, identifiable study data is stolen,

this theft places the participants at greater *risk* of psychological or social harm; this is an unanticipated problem that is not an adverse event. Another example of an unanticipated problem that is not an adverse event is if the FDA announces that one of the study drugs is tainted (e.g., with paint chips), yet no participant experiences any adverse effects.

9.4.5 EVENT RECORDING

The following adverse events will be captured throughout the period of trial participation:

- Protocol-defined (as described above)
- Serious unanticipated events (serious “*Other*” adverse events)

9.4.6 CAUSALITY

The investigator will assess the relationship of an adverse event to the intervention. The investigator should distinguish the relationship between the event and (a) ablation procedure (i.e. AF ablation procedure or other concomitant procedures), and (b) renal sympathetic denervation. Causality will be defined as follows:

Probable

Adverse events that, after careful medical evaluation, are considered with a high degree of certainty to be related to the intervention (AF ablation ± renal sympathetic denervation). The following characteristics will apply:

- A reasonable temporal relationship exists between the event and the intervention, and
- The event is a known reaction to the intervention, and cannot be explained by an alternative etiology commonly occurring in the population/individual.

Possible

Adverse events that, after careful medical evaluation, do not meet the criteria for a probable relationship to the intervention, but for which a connection cannot be ruled out with certainty. The following characteristics will apply:

- The event occurs after intervention, and
- The event is not a known reaction to intervention, but cannot be explained by a commonly occurring alternative etiology

Unlikely

Adverse events that, after careful medical evaluation, do not meet the criteria for a possible or probable relationship to the intervention and for which a connection is unlikely. The following characteristics will apply:

- The event does not follow a reasonable temporal sequence from administration of the intervention, or
- May have been produced by environmental factors, and there is no apparent pattern of response to the intervention.

9.4.7 REPORTING OF SERIOUS ADVERSE EVENTS AND UNANTICIPATED ADVERSE DEVICE EFFECTS

All investigators must report both expected (protocol-defined) and unexpected SAEs. All protocol defined SAEs must be reported directly to the clinical center's IRB and the DCC within 10 business days of knowledge of the event, or as dictated by the specific IRB policy, whichever is sooner. All deaths, UADEs, and unexpected SAEs that are possibly or probably related to the renal sympathetic denervation must be reported to the DCC and the clinical center's IRB within 24 hours of knowledge of the event, or as dictated by the specific IRB policy, whichever is sooner. All *unexpected SAEs* that are *unlikely related to the study intervention* must be reported to the DCC and the clinical center's IRB within 5 business days of knowledge of the event, or as dictated by the specific IRB policy, whichever is sooner.

The DCC will report these events to the DSMB chair within 72 hours of notification. All SAEs will be reported to the DSMB at least semi-annually, at the discretion of the DCC medical monitor.

9.4.8 REPORTING OF UNANTICIPATED PROBLEMS

All *UPs* that are also SAEs, which are at least possibly related to the study intervention, must be reported to the DCC within 24 hours of knowledge of the event. All UPs that are not SAEs must be reported to the DCC within 5 calendar days of knowledge of the event, or as dictated by the specific IRB policy, whichever is sooner.

9.4.9 DCC REPORTING TO FDA

The DCC will report unexpected SAEs that are possibly or probably related to the investigational device or UADEs to FDA as appropriate. The DCC will send an initial IDE safety report communication to the FDA within 2 business days of notification from the site. The DCC will submit a follow-up safety communication to the FDA, based on source documentation or PI Report from the site, within 10 business days from notification of a UADE for this IDE trial.

10. STATISTICAL ANALYSIS PLAN

10.1 STUDY DESIGN

This is a prospective, multi-center, parallel groups, single-blinded, randomized clinical trial. Patients with ischemic or non-ischemic ventricular dysfunction who are to receive an ICD for either 1) secondary prevention, or 2) primary prevention + inducible VT by programmed ventricular stimulation at the time of ICD implantation will be randomly assigned using a 1:1 allocation to treatment to ICD alone or ICD + RSDN. Randomization will be stratified by center.

Our study will include U.S. as well as European sites. We do not anticipate that the two populations will be different. We expect the U.S. population to include 85% Caucasian and the EU population to be 100% Caucasian.

Before conducting the primary analysis we will compare the two populations with respect to baseline characteristics. If a difference is found, the region will be included in all our models as a covariate. We do not anticipate that the treatment effect will be differential in EU and the U.S. This hypothesis will be formally tested using an interaction term in our models.

10.2 PRIMARY OBJECTIVES:

The primary objective is to evaluate the effectiveness of RSDN in the primary prevention of ICD therapy in patients with ischemic or non-ischemic ventricular dysfunction who are to receive an

ICD for either i) secondary prevention, or ii) primary prevention + inducible VT by programmed ventricular stimulation at the time of ICD implantation.

10.3 PRIMARY EFFECTIVENESS ENDPOINT:

The primary effectiveness endpoint is time to first event requiring any ICD therapy (appropriate or inappropriate) or Incessant VT (VT occurring below the ICD rate cut-off); this will be assessed in the on-treatment patient cohort. An event requiring ICD therapy is defined as an anti-tachycardia pacing (ATP) or shock therapy. The null hypothesis of interest is that there will be no difference between the two treatment arms in the time to first event requiring any ICD therapy (appropriate or inappropriate) or Incessant VT in patients randomized to ICD implantation with a single renal sympathetic denervation procedure compared to patients randomized to ICD implantation alone.

10.4 PRIMARY SAFETY OBJECTIVE:

The primary safety objective is to demonstrate that the incidence of serious adverse events (events that cause clinically relevant changes in patient's health, or any event that is life-threatening, results in a fatality, results in permanent disability, requires hospitalization, or prolongs an existing hospital stay) is not increased with the use of the ICD + RSDN compared to ICD alone.

10.5 SECONDARY ENDPOINTS:

The following secondary endpoints will be assessed:

- Appropriate ICD therapy assessed in the full intention-to-treat patient cohort
- Inappropriate ICD therapy
- Number of Hospitalizations for Cardiovascular Causes.
- Total VT burden (Number of episodes).
- All-Cause Mortality.
- The occurrence of ICD storm, defined as ≥ 3 appropriate shock therapies within 24 hours.
- Differences in BUN/creatinine measurements.
- Procedure related adverse events including, but not limited to hematomas, pseudoaneurysms and renal artery stenosis.
- Development of orthostatic hypotension
- 30-day Major Complication Rate defined as death, stroke, MI or any other serious adverse events related to the treatment or procedure within the first 30 days or through hospital discharge (whichever is longer).

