Design:	This study is a prospective, multicenter, single-blinded, randomized (1:1) control trial evaluating the effectiveness of RSDN in the primary prevention of ICD therapy in patients with ischemic or non-ischemic ventricular dysfunction who are to receive an ICD for either i) secondary prevention, or ii) primary prevention + inducible VT by programmed ventricular stimulation at the time of ICD implantation. These patients will be randomized to ICD alone or ICD + RSDN. Subjects will only be eligible for this study if they are \geq 18 years of age and have a history of structural heart disease (post-MI, dilated cardiomyopathy, sarcoid myopathy, hypertrophic cardiomyopathy, etc.), and are planned for ICD implantation for: i. Secondary prevention (e.g.: VT/VF arrest, sustained VT, syncope/inducible VT) ii. Primary prevention + inducible MMVT during induction via ICD lead testing. In addition, eligible patients will have accessible renal vasculature (as determined by renal angiography).
	The patient will be blinded to the results of randomization. Once randomized, study group subjects will undergo a strategy of catheter-based renal sympathetic denervation + ICD implantation (if not already present). Control patients will receive standard ICD implantation alone (if not already present). Follow-up will be conducted in regular intervals over a 12-month period.
Enrollment:	Total: 462 subjects (231 control group, 231 study group)
	An interim safety analysis will be performed after the first 50 subjects (25 control group, 25 study group) have completed their 6-month follow-up visit.
Clinical Sites:	
• Icahn School of Medicine at Mount Sinai• Homolka Hospital, Prague, Czech Republic• Heart Center U SV. Anny Hospital, Brno, Czech Republic• Massachusetts General Hospital• Regional Cardiology, Sacramento, California• Medical University of South Carolina• Florida Hospital, Orlando, Florida

	
 • Other Sites TBD
Time Course:	Enrollment: Over 4 years

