Subject Description:	Eligible subjects include those \geq 18 years of age with a history of structural heart disease (post-MI, dilated cardiomyopathy, sarcoid myopathy, hypertrophic cardiomyopathy, etc.), who are planned for ICD implantation for: i. Secondary prevention (e.g.: VT/VF arrest, sustained VT, syncope/inducible VT) ii. Primary prevention + inducible MMVT during induction via ICD lead testing. iii. Primary prevention + fragmented QRS complex on 12-lead ECG. In addition, eligible patients will have accessible renal vasculature (determined by renal angiography).
Study Group:	In addition to ICD implantation, the subjects in this group will undergo catheter-based renal sympathetic denervation.
Control Group:	Subjects in the control group will undergo standard ICD implantation alone (if not already present).
Primary Endpoint:	Time to first event requiring any ICD therapy (appropriate or inappropriate) or Incessant VT (VT occurring below the ICD rate cut-off); this will be assessed in the on-treatment patient cohort.
Secondary Endpoints:	
 1. Appropriate ICD therapy assessed in the full intention-to-treat patient cohort 2. Inappropriate ICD therapy 3. Number of Hospitalizations for Cardiovascular Causes. 4. Total VT burden (Number of episodes). 5. All-Cause Mortality. 6. The occurrence of ICD storm, defined as \geq3 appropriate shock therapies within 24 hours. 7. Differences in BUN/creatinine measurements. 8. Procedure related adverse events including, but not limited to hematomas, pseudoaneurysms and renal artery stenosis. 9. Development of orthostatic hypotension 10. 30-day Major Complication Rate defined as death, stroke, MI or any other serious adverse events related to the treatment or procedure within the first 30 days or through hospital discharge (whichever is longer);
Primary Analytical Analysis:	Intent to treat analysis
Secondary Analytical Analysis:	Per protocol analysis

Principal Investigator: [name].
Icahn School of Medicine at Mount Sinai
[name]
[name], USA

Site, Monitoring, and Data Management Center Electrophysiology Clinical Research Group
Icahn School of Medicine at Mount Sinai
[name]
[name], USA

Data Safety and Monitoring Board: Chair: [name] (general cardiologist)
[name] (electrophysiologist)
[name] (general cardiologist)
[name] (nephrologist)
[name] (biostatistician)

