9.1.3 RENAL SYMPATHETIC ABLATION PROCEDURAL DETAILS

- Patients will be brought to the electrophysiology laboratory in a fasting state
- Patient sedation or anesthesia will be administered according to standard EP lab protocol.
- Vascular access will be achieved in standard fashion.
- IV heparinization will be instituted. Full systemic anticoagulation will be instituted as per standard hospital procedures to a target ACT of 250 seconds or greater (or equivalent level depending on testing system performed).
- Abdominal aortography will be performed to assess the renal arteries for the suitability of catheter-based renal denervation in all patients. For those patients in whom the angiogram demonstrates that the renal anatomy is inappropriate for the RSDN procedure (small renal arteries, extensive atherosclerosis, renal stenosis, etc.), the patient will be excluded from the study as a screen failure. The patient's baseline information will be collected but no further follow-up required (beyond assessing for any adverse events related to the procedure). If the renal arteries are deemed suitable for RSDN, the patient will then undergo randomization.
- Randomization will be done by permuted-block randomization centrally and will be stratified by site. Allocation concealment shall be maintained at all sites by the use of a web-based central randomization scheme. The operating physician controlling the delivery of ablative energy will be aware of the outcome. This approach has been selected to minimize (1) study bias and (2) placebo effect. The randomization schema will be blocked by size for each site.
- Catheter-based sympathetic renal denervation will be performed using the Vessix balloon ablation catheter for denervation (see image below). The operating physician will manipulate the ablation catheter into the renal arteries as per standard operating procedures.

- The Vessix catheter is available in various sizes, and can be used to treat arteries between 3 mm and 7 mm in diameter and more than 20 mm in length. Radiofrequency energy is delivered via 8 electrodes to four distinct sites within the artery in a bipolar fashion. As with other renal denervation procedures, this catheter delivers four lesions in the artery which are separated along the length of the artery and are also separated orthogonally in different planes (anterior, inferior, posterior, and superior).

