9.2 POST-PROCEDURE

9.2.1 POST-PROCEDURE FOLLOW UP

- All patients will be monitored to verify vascular hemostasis prior to discharge from the hospital.
- All patients will receive either oral aspirin (81-325 mg QD) or clopidogrel (75 mg QD) or warfarin or one of the NOACs (dabigatran, rivaroxaban, Apixaban) for at least 1 week upon discharge.
- Medication and adverse event review will be performed prior to discharge.
- Complications including vascular, stroke, heart failure etc., and presence of ventricular arrhythmias will be documented.
- ICD programming: (see below section 9.2.3)
- The total number of episodes of VT, ATP, and Shocks will be documented at all visits.
- The follow-up includes:
 - 1 Month (\pm 14 days):
 - History and Physical
 - ICD interrogation
 - Office BP measurements (x2) including orthostatics
 - Review of Medications and Adverse events
 - 6 Months (\pm 30 days):
 - History and Physical
 - ICD interrogation
 - Office BP measurements (x2) including orthostatics
 - Lab tests (CBC, Electrolytes, BUN/Cr)
 - BNP Level

- Review of Medications and Adverse Events
 - Repeat Renal Ultrasound or MR/CT Angiography
- 12 Months (\pm 30 days):
 - History and Physical
 - ICD interrogation
 - EKG
 - Office BP measurements (x2) including orthostatics
 - Lab tests (CBC, Electrolytes, BUN/Cr)
 - Blood for Renal Hormones (OPTIONAL)
 - BNP Level
 - Review of Medications and Adverse Events
 - Repeat TTE
- 18 Months (\pm 30 days):
 - History and Physical
 - ICD interrogation
 - Office BP measurements (x2) including orthostatics
 - Review of Medications and Adverse Events
- 24 Months (\pm 30 days):
 - History and Physical
 - ICD interrogation
 - Office BP measurements (x2) including orthostatics
 - Lab tests (CBC, Electrolytes, BUN/Cr)
 - BNP Level
 - Review of Medications and Adverse Events
- 36 Months (\pm 30 days):
 - History and Physical
 - ICD interrogation
 - Office BP measurements (x2) including orthostatics
 - Lab tests (CBC, Electrolytes, BUN/Cr)
 - BNP Level
 - Review of Medications and Adverse Events

Patients will be followed for a maximum of 36 months until the final patient reaches the 18 month follow-up time point. Once the final patient reaches the 18 month follow-up time point, all follow-ups will cease.

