10.9 PRIMARY SAFETY ANALYSIS

The primary assessment of safety will be based on the incidence of all serious adverse events over the total duration of study follow-up. The between group comparisons of incidence of serious adverse events will be estimated using the incidence rate ratio and corresponding 95% confidence intervals based on Poisson regression.

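### The safety rate ratio measures RSDN added to ICD plus renal angiography, so it cannot support the stated conclusion against ICD alone

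*Combined protocol and SAP*

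**What the plan says.** The primary safety objective (Section 10.4) is to demonstrate that SAE incidence "is not increased with the use of the ICD + RSDN compared to ICD alone". The protocol summary describes the control arm in the same terms, in the Design row ("Control patients will receive standard ICD implantation alone (if not already present") and again in the Control Group row ("Subjects in the control group will undergo standard ICD implantation alone (if not already present").

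The procedural sections describe something different:

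- **Sections 8 and 9.1.1:** controls undergo ICD placement and renal angiography. Section 9.1.1 labels them a placebo control, with nothing further done after randomisation.
- **Section 9.1.3:** the steps run from vascular access, to heparin with a target ACT of at least 250 seconds, to imaging ("Abdominal aortography will be performed to assess the renal arteries for the suitability of catheter-based renal denervation in all patients"). Randomisation follows only if the arteries are suitable.
- **Section 9.2.1:** "All patients will receive either oral aspirin (81-325 mg QD) or clopidogrel", or an oral anticoagulant, for at least 1 week. Section 9.1.2 instead ties this treatment to the period after the ablation procedure.

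Section 10.9 bases the primary safety assessment on "the incidence of all serious adverse events over the total duration of study follow-up", with the arms compared by an effect "estimated using the incidence rate ratio and corresponding 95% confidence intervals based on Poisson regression".

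**The concern.** A randomised comparison identifies the effect of whatever differs between the arms. Here that is RSDN alone. Access, aortography and any heparin or antithrombotic treatment are common to both arms. Section 9.4 treats these as real sources of harm: it adds one joint risk list for denervation and angiography, including haematoma, bleeding, vascular injury, renal dysfunction and death, on top of the ICD risk.

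The objective asks a wider question: whether a patient given ICD plus RSDN has more SAEs than a patient given only an ICD. A patient treated with only an ICD has no renal angiogram, and neither arm represents that patient. A ratio near 1 could be reported as meeting Section 10.4 although the trial had not tested the comparison that Section 10.4 names. The RSDN pathway could add access, bleeding or contrast harm without moving the ratio away from 1.

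**Working it through.** **Plan's own figure.** There is none to reproduce. Sections 10.4 and 10.9 state no SAE rate, power or margin for safety. The only usable input is 231 patients per arm (protocol summary, Enrollment). Every rate below is an assumption.

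**Set-up.** Let the expected SAEs per arm of 231, with equal follow-up in both arms, be:

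- B: background from the disease and the ICD;
- C: net addition from access, angiography, heparin and antithrombotic, present in both arms;
- D: addition from RSDN itself, present in one arm.

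Then:

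- ratio the trial estimates = (B + C + D) / (B + C);
- ratio Section 10.4 asks for = (B + C + D) / B;
- difference the trial estimates = D; difference against ICD alone = C + D.

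Dividing the second ratio by the first gives (B + C) / B. The understatement factor on the ratio scale is therefore the same whatever D is. On the difference scale C drops out completely. If D = 0, the trial's expected ratio is 1.00 however large C is.

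**Case D = 0, so the trial ratio is 1.00 in every row.** C is taken as 2 to 12.

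| Background | B per arm | C = 2 | C = 12 |
|---|---|---|---|
| 0.60 per patient | 231 × 0.60 = 138.6 | 140.6 / 138.6 = 1.01 | 150.6 / 138.6 = 1.09 |
| 0.30 per patient | 231 × 0.30 = 69.3 | 71.3 / 69.3 = 1.03 | 81.3 / 69.3 = 1.17 |
| 20 per arm (20 / 231 = 0.087 per patient) | 20 | 22 / 20 = 1.10 | 32 / 20 = 1.60 |

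**Case D > 0, with C = 7 and D = 7.**

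- B = 69.3: the trial shows 83.3 / 76.3 = 1.09; against ICD alone it is 83.3 / 69.3 = 1.20.
- B = 20: the trial shows 34 / 27 = 1.26; against ICD alone it is 34 / 20 = 1.70.

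**Scale against sampling error.** At 0.33 SAEs per patient in each arm (76.2 events), the Poisson standard error of the log ratio is √(2 / 76.2) = 0.162. The 95% interval around a ratio of 1.00 is then about 0.73 to 1.37. The higher-background understatement lies inside that interval, but it is systematic and a larger sample would not remove it.

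**The case against.** The strongest reply is that the comparator is disclosed and that ICD alone is only an arm label. Sections 8 and 9.1.1 state that controls have angiography. Section 9.3 gives its safety expectation against ICD implantation or renal angiography, and the study objective concerns adjunctive RSDN, which this contrast isolates. This stands as a defence of the design. It does not rescue Section 10.4, which uses the label as the reference for a formal safety conclusion.

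A second reply is that absolute information is already planned. Section 10.5 lists procedure-related events and 30-day major complications. Section 10.8 describes all outcome measures and promises 95% confidence intervals. Section 9.3.1 stops the trial if severe procedure-related events exceed 15% of the treatment arm, an absolute rate. This also stands, so it would be wrong to say that safety is judged only by the ratio. But nothing links these items to the conclusion in Section 10.4.

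A reader might infer several stronger claims that the documents do not support:

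- **Shared harms vanish.** On the planned ratio scale they dilute the effect; the ratio is exactly 1.00 only when RSDN adds nothing.
- **All ICD-pocket harm is hidden.** Ordinary pocket harm belongs to ICD alone and should cancel. Only an excess due to heparin or antithrombotics would be masked.
- **The renal artery stenosis reported in Section 3.1 would be missed.** Stenosis caused by energy delivery occurs in one arm only, so the contrast can detect it.
- **The bias always understates harm.** That requires the shared package to be net harmful; antithrombotics could prevent some events.
- **Every control certainly receives arterial access, heparin and an antithrombotic.** Arterial access is inferred from the aortography, and heparin from the order of steps in Section 9.1.3. Sections 9.1.2 and 9.2.1 differ on the antithrombotic.

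**Conclusion.** The point holds as a mismatch between the stated safety conclusion and the comparison that will be observed. The documents settle that controls undergo renal angiography, so the Section 10.9 ratio cannot support a statement against ICD alone. It validly estimates what RSDN adds to ICD plus angiography.

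The size cannot be fixed from the documents. SAEs include any hospitalisation and are counted over the whole of follow-up, so a high background is plausible. At 0.30 to 0.60 SAEs per patient with 2 to 12 shared SAEs per arm, a pathway ratio of about 1.01 to 1.17 would appear as 1.00. The larger 1.10 to 1.60 needs a background as low as 20 SAEs per arm and should not be quoted without that condition. The direction rests on the shared procedure being net harmful.

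A reader might conclude that the angiography control is a design fault. It is not: it isolates RSDN, and it should stay.

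**What to change.** 1. In Section 10.4 and the protocol summary, state the safety contrast as ICD plus renal angiography plus RSDN versus ICD plus renal angiography. Draw no conclusion from the rate ratio that SAEs are not increased relative to ICD alone.
2. In Section 10.9, report for each arm the absolute incidence, with 95% confidence interval, of SAEs that the investigator attributes to vascular access, bleeding or antithrombotic treatment, contrast, or renal artery injury. Show alongside it the procedure-related adverse events that Section 9.1.3 already collects from patients excluded after angiography. Base any statement on added pathway risk over ICD alone on the RSDN-arm absolute rate.
3. Reconcile Sections 9.1.2 and 9.2.1 on which patients receive the post-procedure antithrombotic, and state explicitly which of the pre-randomisation steps in Section 9.1.3 apply to controls.

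No new adjudication is needed. The events committee in Section 9.3.2 handles ICD events only, and Section 9.4.6 already leaves causality to the investigator. Its categories are written around AF ablation and RSDN, so its wording should let the investigator name the angiography procedure. The cost is a text change, one extra table, and a narrower, less favourable safety claim.
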